25.1 Interim Reporting

25.1.1 Reports to independent oversight committees

There are no planned formal interim analyses of outcomes or harms for this trial. There is unlikely to be sufficient power to show benefit, and the interventions are well formulated and tested, and developed to prevent harms. The report to the IDMC at the end of the baseline period will include a re-estimation of the planned sample size. If the study is found to be underpowered, consideration will be given to increasing the number of facilities included.

25.1.2 Assessment of progression criteria

Not applicable.

25.1.3 Formal Interim Analysis

Not applicable.

25.2 Final Analysis

25.2.1 Levels of significance and multiplicity

All applicable statistical tests will be two-sided and will be performed using a 5% significance level; confidence intervals presented will be 95%.

There will be no adjustment for multiplicity. However, results from secondary outcomes will be considered as exploratory and results will be interpreted with caution.

Analyses will be conducted with all clusters assigned to the group they were assigned at randomisation. All observations from randomised facilities (excluding observations from the transition phase) will be included in the analysis.

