4.4 Oversight committees

This study is subject to oversight from the following committees.

International Trial Management Group (TMG): A Trial Management Group (TMG) will be formed comprising the Chief Investigator, other lead investigators (clinical and non-clinical) and members of the LCTC. The TMG are responsible for monitoring all aspects of the progress and conduct of the trial and will be responsible for the day-to-day running and management of the trial. The TMG will meet at least monthly at setup stage and then reduce to quarterly throughout the year unless more frequent meetings are required.

Trial Steering Committee (TSC): The Study Steering Committee will consist of an independent chair, and independent experts in the field of Maternal Health, a biostatistician, including the CI, a lay woman with previous experience of sepsis will participate and observers. The role of the TSC is to provide overall supervision for the study and provide advice through its independent Chair. The decision for the continuation of the study lies with the TSC and as such they will meet throughout the study (at least annually). Terms of reference for the TSC are set out in the TSC Charter.

Independent Data Monitoring Committee (IDMC): The Independent Data Monitoring Committee (IDMC) will consist of an independent chairperson, and independent members, who are experts in the field of Maternal Health and / or Sepsis, and an independent biostatistician. The IDMC will be responsible for reviewing and assessing study progress, conduct and review data. They will assess data quality, including completeness of data, and will review summary characteristics split by treatment group to allow assessment of potential selection bias. The IDMC will first convene prior to the start of recruitment and will then meet at least annually. The Terms of Reference are set out in the IDMC Charter.

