7 STUDY DESIGN

The study is a multi-country, parallel cluster randomised trial with a baseline control phase. There is an integrated implementation evaluation and health economic evaluation. The trial will include 60 clusters, each of which is a health facility (30 in Malawi and 30 in Uganda).

During the first six months each cluster will continue with their current practices and data will be collected to establish weekly rates of maternal infection and mortality experienced which will act as baseline period.

After the baseline period, the clusters will be randomly allocated in a 1:1 ratio to the APT-Sepsis programme or current practice with passive guideline dissemination, using a minimisation algorithm. There will be a three-month transition period during which the APT-Sepsis programme will be introduced to the clusters randomised to the intervention. Data collected during the three-month transition will not contribute to the analysis.

The intervention is delivered at a health facility level and targets the health care providers and systems within the facility. The intervention seeks to change the behaviours of health care providers to improve adherence to WHO guidelines and best practice in infection prevention and management, and detection and management of maternal sepsis.

The post-randomisation phase (including the transition period) will be for a period of twelve months. A detailed understanding of how the intervention is operationalised in practice, will be assessed from a behaviour change perspective.

In the final months of the study, we will complete the data analysis and work with the PPI team and Maternal Sepsis Support groups to disseminate the information about findings.

7.1 **Blinding**

This is an open label study with no blinding requirements. All researchers and participants will know which intervention the cluster has been randomised to the APT-Sepsis programme.

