14 IMPLEMENTATION PERIOD

14.1 Intervention Facilities

Healthcare facilities randomised to the intervention will identify the local Champions who will receive their allocated training (train the trainers training). The Champions will be supported to then roll out the training at the cluster by the HUB team. The APT-Sepsis training package, materials and ongoing support will be provided to each randomised cluster. The healthcare facility will be allowed a transition (set up) period of three months, to complete the delivery of training to all relevant staff, and embed behaviour change and improved practices into routine clinical care.

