15 END OF STUDY

The end of the trial is defined to be the date on which data for all participants is frozen and data entry privileges are withdrawn from the trial database. The trial may be closed prematurely by the Trial Steering Committee (TSC), on the recommendation of the Independent Data Monitoring Committee (IDMC).

Facility closure activities will be centrally coordinated and conducted in accordance with LCTC processes regardless of whether the trial closes as planned or prematurely. This includes activities such as:

- End of Trial notification to REC
- Study-related materials reconciled and returned/disposed of as appropriate.
- All facility data entered onto the study database, discrepancies raised and satisfactory responses received.
- Quality Control checks of the Investigator Site Files and Trial Master File as appropriate.

16 **SAFETY REPORTING**

This trial seeks to implement recognised best practice at a health care setting level. The intervention seeks to improve compliance with WHO guidance and evidence based best practice around infection prevention and management, and therefore improve quality of care and health outcomes.

There are no novel treatments or medications being recommended in this study.

The basis of the intervention is to improve compliance with recognised best practice. These practices are already in use throughout the world, although they are unfortunately not consistently and reliably applied in all settings. Therefore, we do not anticipate adverse events as a direct consequence of the trial.

We recognise that in these settings there will be a range of important adverse outcomes as a consequence of infection and sepsis. Infection-related adverse and non-infection specific outcomes (including death, near miss, severe morbidity and stillbirth and neonatal deaths) data will be measured throughout the study at every facility. Other outcomes, that may potentially be influenced by the intervention, such as caesarean section rates, will also be presented in the IDMC safety report. These outcomes will be monitored by the IDMC and reported by trial arm (the intervention is not blinded). The report content will be detailed in the IDMC charter.

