9.1 Overall study design

A schematic of the trial design can be found in Section 8.1 of the protocol.

This study is a multi-country, two-arm parallel cluster randomised trial with a baseline control phase of at least 6 months, a transition phase of 3 months and a post intervention roll out period of 9 months. The clusters are the health facilities of which we aim to open 64 in total (32 in Malawi and 32 in Uganda). The trial has a cross-sectional design, with different participants in each phase. Data from the transition phase will not be included in the analysis.

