22.2 Safety Analyses

Facilities randomised to APT-Sepsis who do not begin the APT-Sepsis programme will be included in the control safety group. Facilities randomised to control who begin the APT-Sepsis programme will be included in the APT-Sepsis safety group.

23 Facility and patient Characteristics

Characteristics of both the facilities and the included participants will be presented, split by treatment allocation and by time-period (baseline or post intervention roll out). Categorical data will be presented using counts and percentages, continuous data will be presented using mean, standard deviation, median, interquartile range, minimum and maximum. There will be no statistical testing of baseline characteristics.

For characteristics collected weekly, the weekly average at site will be computed and then the average of all sites will be presented. For characteristics collected as available, limited or none, the average proportion of time that they had full availability, limited availability or no availability will be presented.

The following characteristics collected weekly will be presented summarised by facility

- Labour ward theatres in operation
- Functioning autoclaves within the facility
- Equipment available
 - o X-ray
 - Ultrasound facilities
 - FBC testing

LCTC_ST003_TEMP1: SAP Template, V0.1, 08/01/2021

(developed using LCTC_GE001_TEMP4: LCTC Template of a Template, V1.0, 04/09/2020)

- Renal function testing
- Blood culture testing
- Wound swab testing
- Urine microscopy
- Pregnancy tests
- Beds available
- · Beds occupied
- Nurses/midwives working
- Equipment for IV-line insertion
- Working thermometers
- Working BP devices
- Working pulse oximetry machines
- Availability of:
 - Fetoscopes/pinards/fetal stethoscopes
 - o Clocks/watches
 - Spare batteries
 - Urine dipsticks
 - Malaria rapid tests
 - Working O2 concentrators
 - o Bottled or piped O2
 - o Gloves
 - o Soap
 - o Running/flowing water for handwashing
 - Hand drying facilities
 - Alcohol rub for hand cleaning
- Availability of Oral Antibiotics
 - Azithromycin
 - o Amoxicillin
 - o Augmentin
 - Cephalosporin
 - Ciprofloxacin
 - Clindamycin
 - Co-amoxiclav
 - Doxycycline
 - Erythromycin
 - o Flucloxacillin
 - Metronidazole
- Availability of IV antibiotics:
 - o Ampicillin
 - Benzylpenicillin
 - Cefazolin

LCTC_ST003_TEMP1: SAP Template, V0.1, 08/01/2021

(developed using LCTC_GE001_TEMP4: LCTC Template of a Template, V1.0, 04/09/2020)

- Cephalosporin
- Chloramphenicol

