25.2.3.6.2 Analysis

All implementation outcomes are only measured in the post-intervention period, with each site receiving three visits to assess these outcomes. Analysis will focus on the cluster level, with cluster-level outcomes being calculated as proportions at each of the three visits. Analysis will use mixed-effect

repeated-measures linear regression models to compare APT-Sepsis and Control sites. Country, and the minimisation factor facility size will be included as covariates.

26 Safety Evaluations

The primary and secondary outcomes are all related to safety, and other outcomes. Other safety outcomes, that may potentially be influenced by the intervention, such as caesarean section rates, are presented descriptively as described above in the Facility and Patient characteristics section.

27 Additional Analyses

There are no planned additional analyses. We are not collecting information on individual women who did not experience a severe infection, near-miss or maternal mortality therefore a fully covariate adjusted analysis will not be possible.

28 Document History

Statistical Analysis Plan Version	Protocol Version	Section number(s) changed	Description of changes	Justification for changes	Date Implemented
2.0	Malawi: version 6.0 07/11/2024 Uganda: version 3.0 07/11/2024	25.2.3.4.1	Changed the derivation of the outcome to use the patient database rather than the facility database	The derivation was incorrect, the maternal mortality outcome should be based on deaths recorded in the patient database, rather than summary numbers in the facility database.	04/08/2025

29 References

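### The SAP's exclusion of transition data is not limited to efficacy, so the three-month roll-out appears in no by-arm safety table or model in the final report

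*SAP*

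**What the plan says.** **Time after randomisation.** Protocol 7: "The post-randomisation phase (including the transition period) will be for a period of twelve months". SAP 9.1 divides this into "a transition phase of 3 months and a post intervention roll out period of 9 months".

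**What happens in the transition.** Protocol 14.1: "The healthcare facility will be allowed a transition (set up) period of three months, to complete the delivery of training to all relevant staff". The same section expects the new practices to be embedded in routine care by the end of it. Protocol 13 has project officers collecting data throughout the transition in both arms.

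**The exclusion.** SAP 25.2.1: "All observations from randomised facilities (excluding observations from the transition phase) will be included in the analysis". Protocol 7 and SAP 9.1 also leave transition data out of the analysis, again without limiting this to efficacy.

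**The safety evaluation.** SAP 26: "The primary and secondary outcomes are all related to safety, and other outcomes". It refers the remaining safety outcomes, with caesarean rate as the example, to SAP 23. That section presents characteristics "split by treatment allocation and by time-period (baseline or post intervention roll out".

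**The monitoring commitment.** Protocol 16 says that infection-related and other adverse outcomes will be measured for the whole study at every facility, and adds: "These outcomes will be monitored by the IDMC and reported by trial arm".

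**The concern.** Dropping a set-up period is a sound choice for estimating the effect of an established programme. It is not obviously right for harm: staff are being trained and practice is changing during these months, and early problems with a new way of working would be expected to show then. SAP 26 has no safety analysis of its own. It borrows the efficacy outcomes and the descriptive tables, and so takes on their time window. No section gives a reason for applying the exclusion to safety.

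At stake is the completeness of the final safety report. Maternal deaths, near misses, stillbirths, neonatal deaths and caesarean sections during roll-out would be recorded in both arms but not compared in any table. The main safety evidence in this trial is aggregate comparison by arm: no formal interim analysis is planned, and Protocol 16 expects little safety benefit from expedited reporting of single events.

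**Working it through.** **1. Share of post-randomisation time**

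- Transition 3 months and follow-up 9 months (SAP 9.1): 3 + 9 = 12, which reproduces the twelve months in Protocol 7.
- Excluded share: 3/12 = 25%.
- Restoring the transition raises observed post-randomisation time from 9 to 12 months per facility: 3/9 = +33%.

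**2. Births in the excluded period**

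Inputs: at least 1,500 births per facility per year (Protocol 9.1) and 60 facilities, taken as 30 per arm.

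- Check of the births convention: the sample size sections give 750 births per facility in a six-month baseline, and 1,500 × 6/12 = 750.
- Transition births per arm: 30 × 1,500 × 3/12 = 11,250.
- Both arms: 2 × 11,250 = 22,500.

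This is a floor. SAP 16.1 reports more women delivering per cluster than expected. For illustration, take 13 weeks and 15 intervention facilities in each country, all placed at the lower or all at the upper birth cut point of their own country (SAP 12: Malawi 70.8 and 118.5 per week, Uganda 60.5 and 83.9):

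- Lower: 13 × 15 × (70.8 + 60.5) = about 25,600 births.
- Upper: 13 × 15 × (118.5 + 83.9) = about 39,500 births.

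**3. Primary events in the floor of 11,250 births per arm**

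| Rate | Source | Events |
|---|---|---|
| 3% | planning rate, control | 11,250 × 0.03 = 337.5 |
| 2.25% | planning rate, intervention | 11,250 × 0.0225 = 253 |
| 1.96% | baseline cut point, Malawi, read as percent | 11,250 × 0.0196 = 220.5 |
| 3.19% | baseline cut point, Uganda, read as percent | 11,250 × 0.0319 = 359 |

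**4. Where transition data could appear by arm in the final report**

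| Output | Transition by arm? |
|---|---|
| Models for primary and secondary outcomes (SAP 25.2) | No, excluded by 25.2.1 |
| Descriptive tables, including caesarean births (SAP 23) | No, two periods only |
| Recruitment table (SAP 19.1) | No: live births, early losses and stillbirths as totals by facility, not by arm or phase |
| Line graph of outcome rates (SAP 25.2.2.2) | Yes, primary outcome |
| Safety set (SAP 22.2) | Defined by treatment received, but no period and no table attached |

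SAP 22.1 also says that every recorded death, near miss and severe infection at each facility enters the analysis set. That does not sit with SAP 25.2.1, and the SAP does not say which sentence governs the safety evaluation.

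**The case against.** **The period is not wholly hidden.** SAP 25.2.2.2 plans a line graph by arm with the transition marked. This stands, so it would be wrong to say that every safety outcome omits the transition. But the graph is specified for the composite primary outcome. Secondary outcomes are referred to the methods of 25.2.2, so a generous reader might extend the graph to them. The SAP does not say so, the caesarean rate would still be missing, and a graph does not give counts and denominators.

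**The safety set is separate.** SAP 22.2 carries no period limit, so an analyst could include the transition. That is possible, but no output is tied to the set, and the general exclusion in SAP 9.1 would stop most analysts from doing it.

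**Not all of the transition is full exposure.** Training is still being completed, so the 25% is a share of post-randomisation time and not of fully exposed time. This stands.

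**A stronger reading: the IDMC might see no by-arm data after the transition until exposure has ended.** Protocol 4.4 says: "The IDMC will first convene prior to the start of recruitment and will then meet at least annually". With the stated three-month stagger, an immediate data cut and no offset between countries, post-transition data can be reviewed while facilities are still exposed from month 9 to month 21 after the first opening. Annual meetings at exactly months 9 and 21 would miss that window. The documents do not support this as a defect. Meetings at months 0, 12 and 24 fall inside the window if the data lag is under three months, and an end-of-baseline meeting at months 6 to 8 puts the next at months 18 to 20. The annual figure is a minimum: SAP 18.1.1 lets the committees agree the frequency, and report content sits in a charter that is not supplied. SAP 16.1 records that the IDMC itself recommended the shorter follow-up. Nor does any text withhold transition data from the committee; the exclusion governs the final analysis, and Protocol 16 has the IDMC monitoring these outcomes by arm.

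**Conclusion.** The point holds for the final safety report. Followed as written, the SAP leaves 3 of 12 post-randomisation months out of every by-arm safety table and model, although the programme is being delivered and data are collected in both arms. The size is 25% of post-randomisation time: at least 11,250 births per arm, and about 338 primary events per arm at 3% (roughly 220 to 360 across the rates considered). These figures assume 30 facilities per arm and at least the minimum number of births at each. The event range also assumes that the SAP's outcome cut points are percentages.

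This is an incomplete safety report, not an error in the efficacy analysis, where the exclusion is sensible. It is a cheap improvement. No conclusion about the timing or content of IDMC review follows from it.

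**What to change.** In SAP 26:

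1. State that the exclusion of transition data applies to the efficacy analyses only, and align the sentence in SAP 22.1 with this.
2. Add descriptive tables by arm for the transition period, shown separately and also combined with the nine months that follow, for maternal death, near miss, stillbirth, neonatal death and caesarean rate. Give counts and denominators, and say whether the tables use the allocated groups or the safety set of SAP 22.2.

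The efficacy models stay as they are, no test is added and no alpha is spent. The cost is one further set of descriptive tables from data already collected. The downside is that small early differences between arms may be over-read, so the tables should carry a note that they are descriptive, cover a set-up period and are not adjusted for clustering.

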25.2.2 Primary Outcome

The primary outcome is maternal infection related mortality and severe morbidity. This is a composite of infection related maternal mortality, infection related maternal near-miss and severe infection related morbidity (deep surgical site infection or body cavity infection).

Assessments on whether maternal mortality, maternal near-miss or morbidity is infection-related will be made both at site, and by the local hub-team. Should the assessments disagree, an independent review panel will make the final decision.

25.2.2.1 Derivation

A participant will be recorded as having the composite primary outcome if any of the following apply:

- Their reason for inclusion was recorded as severe infection
- Their reason for inclusion was recorded as death or near-miss, and:
 - o both site and hub agree that the cause of the event was infection related OR
- site and hub disagree on whether the cause of the event was infection related, and the independent panel review concluded that it was infection-related
- Their reason for inclusion was near miss, deemed not infection-related by the process above, but experienced a subsequent near miss which was deemed to be infection-related

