To maximise the benefit from this research it is important that the findings inform policy and can therefore impact on practice globally. We are working closely with the WHO that has a vital role in determining health care policy worldwide. We are also collaborating closely with the Ministries of Health in Malawi and Uganda to inform them of the research findings and implications for care and other key international stakeholders such as the Global Sepsis Alliance, International Federation of Gynaecology and Obstetrics (FIGO), International Confederation of Midwives (ICM) and national professional organisations.

6.3 **Objectives**

We will evaluate if implementation of the APT-Sepsis programme is effective at reducing infection-related maternal mortality and severe morbidity through a cluster randomised trial in Malawi and Uganda. We will also conduct a rigorous process evaluation to understand the implementation of the programme and will determine its cost effectiveness.

6.3.1 **Primary Objective**

Primary Objective	Primary Outcome Measures	Timepoint(s) of evaluation
To examine if the APT-Sepsis programme is effective at reducing infection-related maternal mortality and severe morbidity.	The primary outcome is maternal infection-related mortality or severe morbidity. This is a composite of infection-related maternal mortality, infection-related maternal near-miss and severe infection-related morbidity (deep surgical site infection or body cavity infection). The primary outcome will be coded as 1 if any of these components occur, and 0 if none of them occur.	Daily observation of the routine health facility records. From the Preimplementation phase to the end of study. Outcomes will be collected from all women who are admitted to the healthcare facility during pregnancy or within 42 days of delivery. Follow-up of events will occur for up to 28 days until death or discharge from a healthcare facility, whichever is sooner.

See Appendix 1 Near Miss criteria and severe infections definitions.

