APPENDIX 1 Adapted WHO Near Miss Criteria

Operational definitions Section I

The following criteria define a maternal near-miss if they occur during pregnancy, childbirth or within 42 days of pregnancy ending (including birth, abortion or miscarriage).

If one or more criteria are met and the woman survives the case will be counted as a near-miss event.

If the woman subsequently dies during the reporting period, then the case will be classified as a maternal death and not a near-miss event.

Medical events that are considered as near-miss:

Cardiac:

Cardiac Arrest

(Sudden absence of pulse and loss of consciousness)

Cardiopulmonary resuscitation

(A set of emergency procedures including chest compressions and lung ventilation applied in cardiac arrest victims)

Clotting:

Failure to form clots

(The clinical inability to form clots/disseminated intravascular coagulation. Clinically, absence of clotting from the IV site or suture after 7–10 minutes.)

Respiratory:

Gasping

(A terminal respiratory pattern. The breath is convulsively and audibly caught.)

Cyanosis

(A bluish colour of the skin and mucous membranes due to hypoxaemia (insufficient oxygen being carried in the blood).

• Need for invasive ventilation (not due to anaesthesia)

(Requirement for invasive ventilation (mechanical ventilation in which positive pressure is applied to the patient's lungs via an artificial airway device), this does not include provision of oxygen or non-invasive ventilation alone)

Liver:

Jaundice

(Clinically observed yellowing of the skin or sclera (whites of the eyes), raised bilirubin levels do not require laboratory confirmation)

Brain:

• Unconsciousness (not induced by anaesthesia/sedation)

(Any loss of consciousness lasting more than 12 hours, involving complete or almost complete lack of responsiveness to external stimuli. A state compatible with Coma Glasgow Scale <10)

Stroke

(Rapidly developing clinical signs of focal or global disturbance of cerebral function, lasting more than 24 hours)

Paralysis

(The complete or partial paralysis of both sides of the body)

Uncontrollable fit

(Refractory, persistent convulsions. Status epilepticus).

Surgery:

Hysterectomy

(In the maternal near-miss context, surgical removal of the uterus following infection or haemorrhage)

Emergency laparotomy

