25.2.3.1 Components of the composite primary outcome

The three components of the composite primary outcome (infection related maternal mortality, infection related maternal near-miss and severe infection related morbidity (deep surgical site infection or body cavity infection), will each be analysed individually using the methods described in section 25.2.2.

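### The SAP's coding rule for the primary outcome has no path for a severe infection that follows a non-infection near miss, although the protocol counts any component

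*SAP*

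**What the plan says.** Protocol 6.3.1 defines the composite as infection-related maternal death, infection-related near miss, or severe infection-related morbidity. It then gives the coding: "The primary outcome will be coded as 1 if any of these components occur, and 0 if none of them occur". Neither the order of events nor the reason for entry plays a part.

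SAP 25.2.2.1 turns this into three paths to a code of 1:

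- Path 1: "Their reason for inclusion was recorded as severe infection".
- Path 2 begins "Their reason for inclusion was recorded as death or near-miss, and" and requires the cause to be infection-related, by agreement of site and hub or by the independent panel if they disagree.
- Path 3: the woman was included for a near miss judged not infection-related, "but experienced a subsequent near miss which was deemed to be infection-related".

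Only path 3 uses an event after entry, and it names only a near miss.

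Two parts of protocol Appendix 1 matter. Hysterectomy is a near-miss criterion, described as "In the maternal near-miss context, surgical removal of the uterus following infection or haemorrhage", and emergency laparotomy is another. If a woman with a near miss later dies in the reporting period, "then the case will be classified as a maternal death and not a near-miss event".

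SAP 25.2.3.1 says the three components "will each be analysed individually using the methods described in section 25.2.2". It gives no derivation of its own for a component that occurs after entry.

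**The concern.** The protocol asks whether a component occurred. The SAP asks mainly why the woman entered the dataset. The two agree when the first recorded event is the qualifying one. They can part when the first event does not qualify and a later one does.

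The sequence is plausible on the documents' own definitions. A hysterectomy for haemorrhage or an emergency laparotomy brings a woman in as a near miss without infection. Appendix 1 Section II counts a deep surgical-site infection within 30 days of an operation, and protocol 6.3.1 follows events for up to 28 days or until death or discharge. A deep wound infection during the same stay is therefore a protocol primary event. Such infections are also a target of the programme, whose infection-prevention domain includes surgical practice (protocol 6.2).

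At stake is whether the coded primary outcome is the one the protocol defines, and whether the severe-infection component is counted in full.

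**Working it through.** **Step 1. Apply both rules to each sequence.** The inputs are protocol 6.3.1, SAP 25.2.2.1 and protocol Appendix 1. Crossing reason for inclusion, whether that event was infection-related, and the type of later event gives 14 possible combinations. Those that decide the matter are:

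| Entry event | Later event | Protocol | SAP as written | SAP plus Appendix 1 death rule |
|---|---|---|---|---|
| Severe infection | none or any | 1 | 1 | 1 |
| Near miss, infection | none or any | 1 | 1 | 1 |
| Near miss, not infection | none | 0 | 0 | 0 |
| Near miss, not infection | infection-related near miss | 1 | 1 | 1 |
| Near miss, not infection | severe infection | 1 | **0** | **0** |
| Near miss, not infection | infection-related death | 1 | **0** | 1 |
| Death, infection | none | 1 | 1 | 1 |
| Death, not infection | none | 0 | 0 | 0 |

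The literal SAP text disagrees with the protocol in 2 of the 14. If Appendix 1 resets the recorded reason to death, path 2 captures the later death and 1 disagreement remains: the later severe infection. If path 3 covered any later component, there would be none.

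**Step 2. Effect on the relative risk.** Let f be the share of true primary events coded 0. The documents do not give f, so a range of 0.5% to 10% is assumed. Planning rates are 3% and 2.25% (SAP 16.2).

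- Equal f in both arms: RR = 0.0225(1 − f) / [0.03(1 − f)] = 0.75 for every f. At a 3% rate, events lost per 100,000 births = 3,000 × f, from 15 (f = 0.5%) to 300 (f = 10%).
- Unequal f: observed RR = 0.75 × (1 − f for intervention) / (1 − f for control).
  - Control 1%, intervention 2%: 0.75 × 0.98/0.99 = 0.742.
  - Control 5%, intervention 10%: 0.75 × 0.90/0.95 = 0.711.
  - Control 10%, intervention 5%: 0.75 × 0.95/0.90 = 0.792.

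**Step 3. Effect on power when f is equal.** The plan's size reproduces: 1,500 × 23/12 = 2,875 births per facility (750 + 2,125), and × 60 = 172,500.

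For two periods with 30 facilities per arm, let σ² be the mean of p(1 − p) over the arms, b = σ²·ICC·CAC, and v(m) = σ²[ICC + (1 − ICC)/m]. Then V = v(m post) − b²/v(m baseline), SE = √(2V/30), and power = Φ(difference/SE − 1.96).

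With ICC 0.03 and CAC 0.97, σ² = 0.02555 and SE = 0.002405, so power = Φ(0.0075/0.002405 − 1.96) = Φ(1.16) = 87.7%. With monthly periods of 125 births (6 before, 17 after), each phase variance becomes b + [σ²·ICC(1 − CAC) + σ²(1 − ICC)/125]/number of months, and power is 98.7%. The plan's figure of over 95% lies between these and depends on the period structure, so it is not disputed here.

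The revised design is taken as 750 births before and 1,125 after (9 months at the 1,500-a-year minimum), with ICC 0.021 and CAC kept at 0.97. Multiplying both rates by (1 − f) gives:

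| f | Original, two-period | Original, monthly | Revised, two-period | Revised, monthly |
|---|---|---|---|---|
| 0 | 87.7% | 98.7% | 88.9% | 96.9% |
| 2% | 87.0% | 98.6% | 88.2% | 96.6% |
| 5% | 85.9% | 98.3% | 87.2% | 96.1% |
| 10% | 84.0% | 97.8% | 85.4% | 95.2% |

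**The case against.** Four arguments limit the point.

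**Deaths.** A reader might infer that women who later die of infection are also dropped. The documents do not support that. Appendix 1 makes a near miss followed by death a maternal death, and path 2 covers deaths. SAP 25.2.3.4.1 also derives all-cause death from the event details form, without reference to the reason for inclusion. What stands is narrower: SAP 25.2.2.1 does not import the Appendix 1 rule, and does not say that the cause to be judged is then the cause of the death.

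**The form.** The reason for inclusion may accept several values, be updated, or be entered afresh for a later event. No document says. The singular wording, and path 3's contrast between entry and a subsequent event, suggest a single entry-time field but do not prove it. If the field is broader, events may not be lost, but the SAP still needs to say so: its section 5 promises enough detail for replication. SAP 22.1 puts all recorded severe infections in the analysis set, but that settles membership, not coding.

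**A count of lost events.** It is tempting to multiply expected births by an event rate and an assumed share. The documents give no such share. A share of all events following a non-infection near miss would also include later near misses, which path 3 counts, and deaths, which path 2 can count. In addition, follow-up ends at discharge or 28 days, which limits how many later deep infections are seen at all.

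**Bias.** The rule is the same in both arms and both periods, so a biased result cannot be inferred from the rule alone. This stands. Equality is not assured either. If the programme acted mainly on post-operative infection, the missed share would be smaller in its arm and the estimate would move toward 1; better detection could push the other way. The documents fix neither size nor direction.

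**Conclusion.** On its plain reading, SAP 25.2.2.1 departs from the protocol's coding in one sequence: a non-infection near miss followed by a severe infection is coded 0 where the protocol codes 1. Later infection-related death is a missing cross-reference, not a shown loss. SAP 25.2.3.1 has a related gap, since it gives no rule for a component that occurs after entry.

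The size is unknown. Under equal under-counting the relative risk stays at 0.75, and even an assumed 10% loss costs at most about 4 percentage points of power (87.7% to 84.0%). Any bias depends on a difference between arms that the documents neither show nor exclude.

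Confidence is moderate, because the loss depends on the reason for inclusion being a single value fixed at entry. The point should be fixed before the comparative analysis, since changing primary-outcome coding afterwards would be open to the charge of a post hoc choice. It does not by itself threaten the trial's conclusion.

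**What to change.** 1. Reword the last path of SAP 25.2.2.1. A woman included for a near miss judged not infection-related should be coded 1 if, later in the follow-up window, she has an infection-related near miss, a severe infection meeting Appendix 1 Section II, or an infection-related death.
2. State that a near miss followed by death is classified as a death, as in Appendix 1, and that infection-relatedness is then judged on the death.
3. State whether the reason for inclusion holds one value or several, and whether it is updated.
4. In SAP 25.2.3.1, derive each component from all events recorded for the woman.

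The core change is one sentence and an edit to the derivation program; the other items are short clarifications. No new data are needed if later events are already recorded. The form evidently captures a subsequent near miss, so the trial team should confirm that it also captures a subsequent severe infection.
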